10.4.2.2. Safety Analyses

Safety data, including all AEs (i.e., non-serious, serious and AEs of special interest), laboratory data, vital signs, concomitant medications and meeting protocol defined

stopping criteria (e.g., liver chemistry) will be descriptively summarized by treatment arm. Reasons for stopping randomized treatment and for early study withdrawal will also be summarized by treatment group and time to stopping treatment or study will be presented graphically and assessed. Full details of all safety data reporting will be described in the RAP.

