If the AE onset date/AE worsening and/or resolution date is missing or incomplete in the database for any occurrence of the specific AE, time to first onset/worsening and/or duration of the first, second, and third occurrence will be left missing for the participant. These summaries of special interest AEs will be provided for those AEs classified as treatment emergent.

Adverse Events

The number, percentage, and exposure-adjusted AE incidence rate per 100 person-years of participants reporting at least one AE will be provided for each treatment group. These events will be summarized by treatment group, primary system organ class, and preferred term. Similarly, the number and percentage of participants reporting at least one follow-up AE will be summarized by treatment group, primary system organ class, and preferred term.

In addition, all treatment emergent AEs will be summarized by treatment group, primary system organ class, higher level term and preferred term. In addition to generating number and percentage of subjects with treatment emergent SAEs, relative risk and 95% Wald confidence intervals will be presented for each HLT and PT as described in Section [10.6.4](#).

Summaries of all treatment emergent AEs will be produced for the following subgroups - age group, gender, race group, and weight quartile- by treatment group, primary system organ class, and preferred term.

A listing of AE records for all participants who reported AEs will be produced.

The number and percentage of participants reporting the most common treatment emergent AEs (those occurring in $\geq 5\%$ of participants in any treatment group) will be summarized by preferred term and treatment group.

The number and percentage of participants reporting treatment emergent AEs assessed by the investigator to be related to the study drug (termed as drug-related hereafter) will be summarized by treatment group, primary system organ class, and preferred term.

The number and percentage of participants reporting treatment emergent AEs by maximum intensity will be summarized by treatment group, primary system organ class, and preferred term.

The number and percentage of participants reporting treatment emergent drug-related AEs by maximum intensity will be summarized by treatment group, primary system organ class, and preferred term.

A listing of which participants reported specific adverse events will be produced.

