The hierarchical relationship between MedDRA SOCs, PTs and verbatim text will be listed for all adverse events.

The number and percentage of participants and the number of occurrences of common non-serious treatment emergent adverse events (those occurring in $\geq 5\%$ of participants in any treatment group) will be summarized by primary system organ class, preferred term, and treatment group.

CONFIDENTIAL

205270

The number and percentage of participants with treatment emergent non-serious drug-related adverse events will be summarized by primary system organ class, preferred term, and treatment group and separately by overall frequency

Serious and Other Significant Adverse Events

The number and percentage of participants and the number of occurrences of treatment emergent SAEs will be provided for each treatment group. These events will be summarized by treatment group, primary system organ class, and preferred term. Follow-up SAEs will be summarized similarly.

Additionally, a tabular display of exposure-adjusted AE incidence rate per 100 person-years of participants reporting at least one SAE will be produced by treatment group, primary system organ class, and preferred term.

All treatment emergent SAEs will also be summarized by treatment group, primary system organ class, higher level term and preferred term. In addition to generating number and percentage of subjects with TE SAEs, relative risk and 95% Wald confidence intervals will be presented for each HLT and PT as described in Section 10.6.4.

A listing of reasons for considering as a SAE will be produced for all treatment emergent SAEs.

The number and percentage of participants with treatment emergent drug-related SAEs will be summarized by treatment group, primary system organ class and preferred term.

The number, percentage, and exposure-adjusted AE incidence rate per 100 person-years of participants with fatal AEs will be provided for each treatment group. These events will be summarized by treatment group, primary system organ class, and preferred term.

Additionally, the number and percentage of participants with treatment emergent serious, fatal and non-fatal, drug-related AEs will be summarized by treatment group and overall frequency.

A listing of treatment emergent fatal SAE records and a listing of treatment emergent non-fatal SAE records will be provided.

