| 
 ● Relative risk and 95% confidence interval will be calculated as follows: Relative Risk (RR) = pd / pc Lower limit of 95% CI = $RR * \exp[-z * (v)^{1/2}]$ Upper limit of 95% CI = $RR * \exp[z * (v)^{1/2}]$, where $v = \text{Variance}[\ln(RR)] = [(1-pc) / nc1] + [(1-pd) / nd1]$ nc : number of subjects in placebo group nd : number of subjects in daprodustat group nc1 : number of subjects with AE in placebo group nd1 : number of subjects with AE in daprodustat group pc : proportion of subjects with AE in placebo group = $nc1 / nc$ pd : proportion of subjects with AE in daprodustat group = $nd1 / nd$ 
 ● z : 97.5th percentile of the standard normal distribution |

Order of CV Safety Endpoint Events

- If multiple events occur on the same day or have imputed dates that place them on the same day, but it is not clear which event occurred first, then the following order will be applied:
 1. MI
 2. Stroke
 3. Hospitalization for Heart Failure

CONFIDENTIAL

205270

Order of CV Safety Endpoint Events

4. Thromboembolic Event: DVT
5. Thromboembolic Event: VAT
6. Thromboembolic Event: PE
7. Death

Laboratory Parameters

- If a laboratory value which is expected to have a numeric value for summary purposes, has a non-detectable level reported in the database, where the numeric value is missing, but typically a character value starting with '<x' or '>x' (or indicated as less than x or greater than x in the comment field) is present, the number of significant digits in the observed values will be used to determine how much to add or subtract in order to impute the corresponding numeric value.
 - Example 1: 2 Significant Digits = '< x' becomes $x - 0.01$
 - Example 2: 1 Significant Digit = '> x' becomes $x + 0.1$
 - Example 3: 0 Significant Digits = '< x' becomes $x - 1$
- If a laboratory value which is expected to have a numeric value for summary purposes, has a non-detectable level reported in the database, where the numeric value is missing, but typically a character value starting with '≤x' or '≥x' is present, then the corresponding numeric value will be set equal to x.
- If there is more than one laboratory value on the same date for the same laboratory test, then the laboratory values associated with scheduled visits will be used.
- The following will be used to convert laboratory values from SI units to conventional units [Iverson, 2007]:

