10.10.2. Mock Example Shell Referencing

Non IDSL specifications will be referenced as indicated and if required example mock-up displays provided in [Appendix 11](#): Example Mock Shells for Data Displays.

| Section | Figure | Table | Listing |
|------------------|----------------|-----------------|------------|
| Study Population | - | Shell 1 - 30 | - |
| Efficacy | EFF_F1- EFF_F4 | EFF_T1- EFF_T50 | - |
| Safety | Shell 3.4-3.7 | Shell 1-50 | Shell 1-12 |

NOTES:

- Non-Standard displays are indicated in the 'IDSL / Example Shell' or 'Programming Notes' column as '[Non-Standard] + Reference.'

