10.10.8. Safety Tables

| Safety: Tables | | | | | |
|-----------------------------|------------|----------------------|---|--|-------------|
| No. | Population | IDSL / Example Shell | Title | Programming Notes | Deliverable |
| Adverse Events (AEs) | | | | | |
| 3.1. | Safety | Shell 32 | Summary of All Treatment Emergent Adverse Events by System Organ Class and Preferred Term | ICH E3 Add exposure-adjusted AE incidence for both treatments | DR, SAC |
| 3.2. | Safety | Shell 32 | Summary of All Treatment Emergent Adverse Events by System Organ Class, Higher Level Term, and Preferred Term | ICH E3 | DR, SAC |
| 3.3. | Safety | Shell 32 | Summary of All Follow-Up Adverse Events by System Organ Class and Preferred Term | ICH E3 | DR, SAC |
| 3.4. | Safety | Shell 33 | Summary of Common ($\geq 5\%$) Treatment Emergent Adverse Events by Overall Frequency | ICH E3 | DR, SAC |

CONFIDENTIAL

205270

| Safety: Tables | | | | | |
|-----------------------|-------------------|-----------------------------|--|----------------------------|--------------------|
| No. | Population | IDSL / Example Shell | Title | Programming Notes | Deliverable |
| 3.5. | Safety | Shell 32.1 | Summary of All Treatment Emergent Adverse Events by Maximum Intensity by System Organ Class and Preferred Term | ICH E3 | DR, SAC |
| 3.6. | Safety | Shell 32 | Summary of All Drug-Related Treatment Emergent Adverse Events by System Organ Class and Preferred Term | ICH E3 | DR, SAC |
| 3.7. | Safety | Shell 32 | Summary of All Serious Drug-Related Treatment Emergent Adverse Events by System Organ Class and Preferred Term | | DR, SAC |
| 3.8. | Safety | AE20 | Summary of Treatment Emergent Serious Fatal and Non-Fatal Drug-Related Adverse Events by Overall Frequency | Page by fatal vs non-fatal | DR, SAC |
| 3.9. | Safety | Shell 32 | Summary of All Non-Serious Drug-Related Treatment Emergent Adverse Events by System Organ Class and Preferred Term | | DR, SAC |
| 3.10. | Safety | Shell 33 | Summary of All Non-Serious Drug-Related Treatment Emergent Adverse Events by Overall Frequency | | DR, SAC |
| 3.11. | Safety | Shell 34 | Summary of Common ($\geq 5\%$) Non-serious Treatment Emergent Adverse Events by System Organ Class and Preferred Term (Number of Subjects and Occurrences) | FDAAA, EudraCT | DR, SAC |
| 3.12. | Safety | Shell 32.1 | Summary of All Treatment Emergent Drug-Related Adverse Events by System Organ Class and Preferred Term and Maximum Intensity | ICH E3 | DR, SAC |

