| 3.13. | Safety | Shell 32 | Summary of All Treatment Emergent Adverse Events by System Organ Class and Preferred Term by Race | | DR, SAC |
| 3.14. | Safety | Shell 32 | Summary of All Treatment Emergent Adverse Events by System Organ Class and Preferred Term by Age | | DR, SAC |
| 3.15. | Safety | Shell 32 | Summary of All Treatment Emergent Adverse Events by System Organ Class and Preferred Term by Gender | | DR, SAC |

CONFIDENTIAL

205270

| Safety: Tables | | | | | |
|---|------------|----------------------|---|--|-------------|
| No. | Population | IDSL / Example Shell | Title | Programming Notes | Deliverable |
| 3.16. | Safety | Shell 49 | Summary of Treatment Emergent Adverse Events of Special Interest by Preferred Term | Add exposure-adjusted AE incidence for both treatments | DR, SAC |
| 3.17. | ITT | Shell 1 | Summary of First-Occurrence of Adjudicated MACE | | DR, SAC |
| 3.18. | ITT | Shell 3 | Summary of All Adjudicated MACE | | DR, SAC |
| 3.19. | ITT | Shell 1 | Summary of First Occurrence of Adjudicated MACE or Thromboembolic Events or Hospitalization for Heart Failure | | DR, SAC |
| 3.20. | ITT | Shell 3 | Summary of All Adjudicated MACE or Thromboembolic Events or Hospitalization for Heart Failure | | DR, SAC |
| Serious and Other Significant Adverse Events | | | | | |
| 3.21. | Safety | Shell 34 | Summary of Serious Treatment Emergent Adverse Events by System Organ Class and Preferred Term (Number of Subjects and Occurrences) | FDAAA, EudraCT | DR, SAC |
| 3.22. | Safety | Shell 32 | Summary of Serious Treatment Emergent Adverse Events by System Organ Class, Higher Level Term, and Preferred Term | ICH E3 | DR, SAC |
| 3.23. | Safety | Shell 34 | Summary of Serious Follow-Up Adverse Events by System Organ Class and Preferred Term (Number of Subjects and Occurrences) | FDAAA, EudraCT | DR, SAC |
| 3.24. | Safety | Shell 32 | Summary of Treatment Emergent Adverse Events Leading to Permanent Discontinuation of Study Treatment by System Organ Class and Preferred Term | IDSL Add exposure-adjusted AE incidence for both treatments | DR, SAC |
| Laboratory: Chemistry | | | | | |
| 3.25. | Safety | Shell 16 | Summary of Post-randomization Chemistry Change from Baseline | ICH E3 | DR, SAC |
| 3.26. | Safety | Shell 36 | Summary of Worst Case On-treatment Chemistry Results PCI Criteria Post-Baseline Relative to Baseline | ICH E3 | DR, SAC |

CONFIDENTIAL

205270

| Safety: Tables | | | | | |

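### The planned SAE relative risk by HLT and PT does not exist when placebo has no event, so a daprodustat-only term gets no between-arm estimate or interval

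*SAP*

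**What the plan says.** SAP 8.2, in the paragraphs on serious events, commits to "percentage of subjects with TE SAEs, relative risk and 95% Wald confidence intervals will be presented for each HLT and PT as described" in SAP 10.6.4. The display is Table 3.22, "Summary of Serious Treatment Emergent Adverse Events by System Organ Class, Higher Level Term, and Preferred Term".

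SAP 10.6.4 gives the calculation: "Relative Risk (RR) = pd / pc", where pd and pc are the proportions of subjects with the event on daprodustat and placebo. The limits are RR × exp(±z√v), with v = (1−pc)/nc1 + (1−pd)/nd1, where nc1 and nd1 are the numbers of subjects with the event. It states no continuity correction, score or exact interval, minimum count, or rule for an empty cell.

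Scope is less clear for all treatment-emergent AEs. The AE paragraph of SAP 8.2 describes the HLT and PT summary (Table 3.2, "Summary of All Treatment Emergent Adverse Events by System Organ Class, Higher Level Term, and Preferred Term") and then continues: "In addition to generating number and percentage of subjects with treatment emergent SAEs, relative risk and 95% Wald confidence intervals will be presented". It names SAEs where AEs are probably meant.

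Protocol 10.4.2.2 says only that safety data "will be descriptively summarized by treatment arm".

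**The concern.** The plan promises a statistic for every term, but its own formula cannot always supply one. It fails for the pattern a rare drug-specific toxicity would produce: several events on daprodustat and none on placebo. This ratio is also the only between-arm AE estimate for which the SAP gives a formula. The other SAE and AESI tables described are per arm (counts, percentages, occurrences, exposure-adjusted rates), and the only absolute rate difference with an interval is for the rescue endpoint.

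The result is an awkward ordering. A split of 6 v 1 prints a relative risk and an interval; the more extreme 6 v 0 prints nothing. Empty comparator cells are also foreseeable: the risk table in Protocol 3.3.1 reports thrombosis with excessive erythropoiesis as 3/688 v 0/404 with no ratio, although most AESI categories in that table carry one.

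**Working it through.** The documents give no figure for this point, so there is none to reproduce.

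**Inputs.** Formulas from SAP 10.6.4. Arm size n = 300 from Protocol 10.2.1; the Safety Population could be slightly smaller. No per-term event rates are given, so the rates below are assumptions shown over a range.

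**1. The formula with an empty arm.**
- nc1 = 0: pc = 0, so RR = pd/0, and v contains 1/0. Neither RR nor interval exists, whatever the daprodustat count.
- nd1 = 0 with nc1 > 0: RR = 0, and v contains 1/0. No interval exists.
- For contrast, 6 v 1: RR = 6.0, v = (1 − 1/300)/1 + (1 − 6/300)/6 = 0.9967 + 0.1633 = 1.16, interval 6 × exp(±1.96 × √1.16) = 0.73 to 49.5.

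**2. How often one arm is empty under equal rates.** Let q = (1−p)^300. Among terms with at least one event, the share with exactly one arm empty is 2q(1−q)/(1−q²); half of that share is daprodustat-only.

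| True rate p | q | One arm empty: no interval | Daprodustat-only: no RR either | Three or fewer events, given one arm empty |
|---|---|---|---|---|
| 0.2% | 0.548 | 71% | 35% | 99% |
| 0.5% | 0.222 | 36% | 18% | 92% |
| 1.0% | 0.049 | 9% | 5% | 63% |

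If the HLT contains a second PT at the same rate, an HLT-level ratio exists with probability 1−q, that is 45%, 78% or 95%.

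**3. What a measure defined at zero would show.** Newcombe risk difference (daprodustat − placebo). With zero placebo events the Wilson upper limit for placebo is 1.26%. For 5 v 0, p = 1.67% with Wilson limits 0.71% and 3.84%. The lower limit is 1.67 − √((1.67 − 0.71)² + 1.26²) = 0.08, and the upper is 3.84.

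| Split | Risk difference, % | 95% CI, % |
|---|---|---|
| 1 v 0 | 0.33 | −0.96 to 1.86 |
| 2 v 0 | 0.67 | −0.69 to 2.40 |
| 3 v 0 | 1.00 | −0.43 to 2.90 |
| 4 v 0 | 1.33 | −0.17 to 3.38 |
| 5 v 0 | 1.67 | 0.08 to 3.84 |
| 6 v 0 | 2.00 | 0.34 to 4.29 |
| 8 v 0 | 2.67 | 0.85 to 5.17 |

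The interval first excludes zero at 5 v 0.

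**4. How likely a split of 5 or more v 0 is.** The probability is P(nc1 = 0) × P(nd1 ≥ 5).
- Equal rates of 0.2%, 0.5% or 1.0%: 0.02%, 0.4% or 0.9% per term against daprodustat; 0.04%, 0.8% or 1.8% counting both directions.
- Placebo 0.1%, so P(nc1 = 0) = 0.741. Daprodustat 0.5%: 0.741 × 0.018 = 1.4%. Daprodustat 1%: 0.741 × 0.184 = 14%. Daprodustat 2%: 0.741 × 0.718 = 53%. Daprodustat 3%: 0.741 × 0.948 = 70%.

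**The case against.** Any ratio fails with an empty comparator, so this can be read as a preference for another measure. Safety is descriptive and outside the testing hierarchy. With no placebo event the risk difference is simply the daprodustat percentage, which the plan already prints, and a reader could compute the interval from the counts. Listings, grouped AESI tables and adjudicated MACE tables also show one-sided events. All of this is true, and it keeps the point small.

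The size depends on the assumed effect. The 14% to 70% figures need a 10- to 30-fold increase. At 0.5%, the level of the 3/688 example, the figure is 1.4%. The 5 v 0 threshold also depends on the method: the two-sided Fisher p-value there is 0.06, while a Miettinen-Nurminen interval already excludes zero at 4 v 0 (0.06% to 3.38%). More unadjusted intervals on sparse terms could mislead as well as inform. These points stand as cautions on how the column is labelled and read.

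The sponsor's data standards and the table and figure shells are not in the text available. SAP 10.10.2 says of the shells: "Non IDSL specifications will be referenced as indicated and if required example mock-up displays provided in" Appendix 11. They may already print not estimable. That would settle the display convention, but it would still leave 6 v 0, or 8 v 0 (Fisher p = 0.007), with no interval.

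**Conclusion.** The concern holds. As written, the plan cannot give the promised relative risk and interval for a daprodustat-only SAE term, or the interval for a placebo-only term, and it specifies no substitute. The event itself is not hidden, and most affected rows hold counts too small for any interval to say much. The practical loss is confined to splits of about 5 or more v 0: rare under equal rates (at most 0.9% per term against daprodustat in the range examined), but quite likely if the drug multiplies a rare risk tenfold or more. These figures rest on 300 per arm and assumed event rates. For all treatment-emergent AEs the same gap follows only if the AE paragraph of SAP 8.2 is meant to cover AEs. This is a worthwhile minor improvement.

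**What to change.** In SAP 8.2 and 10.6.4, add for each HLT and PT in Table 3.22 a risk difference (daprodustat − placebo) with a Newcombe score 95% interval, stated to be descriptive and unadjusted for multiplicity. Keep the relative risk and Wald interval where both arms have at least one event, and print not estimable otherwise. Settle whether the AE paragraph of SAP 8.2 means AEs or SAEs; if AEs, correct the word and apply the same rule to Table 3.2. Fix the rule before unblinding, so that the zero-cell method is not chosen after seeing which terms are one-sided.

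The cost is SAP wording and one extra column in one or two tables, with no new data. The downside is wider tables and more intervals on sparse terms. Under equal rates, the chance that a one-arm-empty row would show an interval excluding zero is the both-directions figure above, at most 1.8% per term.

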8.3. Clinical Laboratory Analyses

Clinical chemistry, hematology and other laboratory tests are assessed in this study according to the schedule outlined in the Schedule of Activities (see Section 10.2.1) and include the following tests:

| Laboratory Assessments | Parameters | | |
|--|---|---------------------------------------|-------------------------------------|
| Hematology | Platelet count | RBC indices: | WBC count with Differential: |
| | RBC count | MCV | Neutrophils |
| | Reticulocyte count | MCH | Lymphocytes |
| | Hgb | MCHC | Monocytes |
| | Hematocrit | RDW | Eosinophils |
| | | | Basophils |
| Clinical Chemistry ¹ | Sodium (serum) | Aspartate aminotransferase (AST) | Carbon Dioxide (total) |
| | Potassium (serum) | Alanine aminotransferase (ALT) | Albumin |
| | Calcium (total and albumin-adjusted) | Inorganic phosphate | Urea (serum) |
| | Creatinine (serum) | Bilirubin (total and direct/indirect) | Chloride (serum) |
| | eGFR | | |
| Iron parameters | Iron (serum) | Ferritin | UIBC |
| | Hepcidin | TIBC | TSAT |
| Lipid parameters | Total cholesterol | LDL-C (direct) | HDL-C |
| Other laboratory tests | Urine/serum hCG pregnancy test ^{2,3} | FSH ⁴ | Estradiol ⁴ |
| | HemoCue Hgb | hsCRP | |

WBC, white blood cells; MCV, mean corpuscular volume; MCH, mean corpuscular hemoglobin; MCHC, mean corpuscular hemoglobin concentration; RDW, red blood cell distribution width, AST, aspartate transaminase; LDL-C, low density lipoprotein-C; HDL-C, high density lipoprotein-C; TIBC, total iron binding capacity; hCG, human chorionic gonadotropin; FSH, follicle-stimulating hormone.

1. Details of Liver Chemistry Stopping Criteria and Required Actions and Follow-Up Assessments after liver stopping or monitoring event are given in Section 8.1.1 and Appendix 6 the protocol.
2. For women of childbearing potential only.
3. Local urine testing will be standard for the protocol unless serum testing is required by local regulation or IRB/IEC, and for participants who transition to dialysis during the study.
4. Screening only. As needed for postmenopausal women when their menopausal status is in doubt. See Inclusion Criteria Section 6.1 of the protocol.

Summaries of central laboratory Hgb values, HemoCue Hgb values, iron parameter values (serum iron, ferritin, hepcidin, TIBC, TSAT) are included in earlier efficacy sections and will not be included with clinical laboratory displays. However, these parameters may be included in PCI summaries.

The clinical chemistry tests performed in this study include ALT, AST and bilirubin. In addition to being summarized with the clinical chemistry values, these laboratory values will be included in some of the Hepatobiliary (liver) displays.

In addition to the visits listed for the laboratory assessments in the Schedule of Activities (see Section 10.2.1), any of these assessments can be performed at an unscheduled/retest visit or at the follow-up visit at the discretion of the investigator. See Section 10.5.2 for handling of unscheduled values. The laboratory's normal range values will be provided by the central laboratory and potential clinical importance thresholds are defined in Section 10.8.1.

All of the tabular summaries described below will include summaries in SI units; conventional units will also be provided for the following laboratory tests: hemoglobin, MCHC, total calcium, albumin-adjusted calcium, inorganic phosphate, albumin, urea, total cholesterol, LDL-C, HDL-C, and eGFR. Conversions from SI units to conventional units are included in Section 10.6.4.

eGFR equation is outlined in Section 10.6.4.

The clinical laboratory safety analyses will be based on the Safety population and GSK Core Data Standards, unless otherwise specified. The details of the planned displays are in [Appendix 10: List of Data Displays](#).

